#### Visit 1 (V1) - (Day 1): Screening/Inclusion/Randomization

Subjects with symptoms of acute infectious rhinitis for  $\leq 48h$  will go to the site for the screening/inclusion visit (visit 1). The investigator will give oral information relative to the study and will answer all questions relative to the study participation. The patient will receive the information sheet. If the subject agrees to participate in the study, he/she will be asked to give a written consent.

Each screened subject will be assigned a subject identifier number during screening that will be used on all subject documentation. The subject identifier number will contain the site number and the subject number and will be assigned in numerical order at the screening visit based on chronological order of screening dates (e.g., 001-010 for the 10th subject screened at the Site #001).

The investigator or his/her delegated designee will:

- Record demographic data, medical history and ongoing medication.
- Perform a physical and clinical examination. A pharyngeal nasal swab will be performed by the investigator or by the delegated study nurse to check for absence or presence of SARS-CoV2.
- Verify that eligibility criteria are fulfilled.
- Record the score of the common cold symptoms (headache, muscle ache, chilliness, sore throat, blocked nose, runny nose, cough, sneezing according to a physician-rated symptom score after clinical examination; (scale: 0  $\rightarrow$  3 [0: no symptom, 1 = mild symptoms (sign/symptom clearly present, but minimal awareness; easily tolerated), 2 = moderate symptoms (definite awareness of sign/symptom that is bothersome but tolerable), 3 = severe symptoms (sign/symptom that is hard to tolerate; causes interference with activities of daily living and/or sleeping]). This scoring system was developed by Jackson in 1958 and is widely used in common cold clinical trials [14].
- Review and detail the question of the WURSS-21.
- Allocate a treatment number for eligible subjects via the eCRF.
- Explain how to complete every day the e-diary for WURSS-21 recording, how to report concomitant medications, adverse events/incidents/expected undesirable side effects. The patient will access the e-diary application using a smartphone.

*NB: The first WURSS-21 will be completed by the subject on site during this visit after the randomization of the patient.*

- Remind the patient to return the device for assessment of compliance to the treatment at V2.

The investigator will provide the patient with the device according to the treatment number as per randomization and explain how to use it. The investigator will also prime the pump bottle to identify a

**Strictly Confidential**

possible malfunction before the patient leaves the site. In case of dysfunction, a new randomisation number and a new treatment will be attributed to the patient using the eCRF back-up randomisation module.

*NB: The first use of the device will be performed in the evening of the Day 1.*

**D1-D8 (at home):**

The patient will be asked to complete the electronic diary daily (WURSS-21 assessed once daily in the evening, taking into account the symptoms from the morning to the evening, adverse events/incidents/expected undesirable side effects and concomitant medications).

**D8 (Telephone Call):**

The investigator or his/her delegated designee will call the patient to remind him/her to stop the treatment.

➤ *NB: The last study nasal spray intake will be performed in the morning of the Day 8.*

**D9-D13/15 (at home):**

Patients will continue to complete the electronic diary daily (incidents/adverse events in relation with the common cold, concomitant medications). The patient for whom common cold symptoms persist, will be instructed to continue to complete the WURSS-21, until the subject feels not sick for two consecutive days.

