Objectives:	
Primary Objective:
 
 
- To compare the efficacy of Healsea® Rescue* and Placebo to improve the Quality of Life through symptoms of acute infectious rhinitis reduction in adults during a 7-day treatment period.
 
 
Secondary objectives:
 
 
- To compare the efficacy of Healsea® Rescue* and of the Placebo to reduce the duration of each infectious rhinitis symptoms rated by the WURSS 21
 
- To compare the efficacy of Healsea® Rescue* and of the Placebo to reduce the use of concomitant medication (antipyretics, systemic or local mucolytics, decongestants, antitussives, antibiotics)
 
- To compare the subject overall assessment on efficacy of Healsea® Rescue* and of the Placebo.
 
- Safety: to assess systemic and local tolerance of Healsea® Rescue* over the study period.
 

Endpoints:	
Primary Endpoint:  The primary endpoint is the AUC of Wisconsin Upper Respiratory Symptom Survey (WURSS-21) during first 8 days of symptoms.  The WURSS-21 will be assessed once daily during D1-D8.
 
Secondary Endpoints:
 
 
- AUC of the symptoms sub-score (items 2-11) and Quality of Life sub-score (items 12-20) of the WURSS-21 during first 8 days.
 
- Duration of cold symptoms in both groups assessed by means of the WURSS-21.  For each item, the duration is defined as the number of symptomatic days between D1 and the first day the subject reports not having the symptom for two consecutive days.  Notice that the duration may be censored at day 13-day 15.
 
- Frequency and number of days of use of concomitant treatments that may affect common cold symptoms (antipyretics, systemic or local mucolytics, decongestants, antitussives, antibiotics).
 
- Subject satisfaction regarding ease of use, efficacy, local tolerance and taste at the end of study visit (V2) using a 4-points categorical scale and of Global subject feedback on treatment use ("will you recommend the prescribed treatment for treatment of acute rhinitis?").
 
- Safety: Assessment of adverse events/incidents/foreseeable side effects throughout the study in both groups
 

Indication:	Treatment of acute rhinitis

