## 2. Flow Chart

Visit name	Acute phase		Telephone call	Follow-up	
	Screening/Inclusion	At home		At home	End of study
Visit Number	V1		TC1		V2
Days/Weeks	D1	D1-D8	D8	D9-End of study visit	D13-D15
Informed consent	X				
Eligibility criteria	X				
Demography and Medical history	X				
Physical and clinical examination	X				X
COVID-19 antigen test	X				X
Ongoing medication	X				
Randomization	X				
Treatment ( Healsea® Rescue* or Placebo) (14 intakes)		X			
Telephone call (End of Healsea® Rescue* or Placebo)			X		
Subject e-diary and WURSS 21	X*	X		X §	X*
(Serious) Adverse Events/ (serious) incidents and concomitant medication reporting	X	X		X	X
Satisfaction Questionnaire					X
Compliance					X

§ After D8, WURSS-21 until complete resolution of symptoms for 2 consecutive days.

\*WURSS-21 to be completed with the investigator on site at screening and at the end of the study if the patient still has not ticked "not sick" for 2 consecutive days in the previous days.

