### 6.3 Secondary Objectives

- To compare the efficacy of **Healsea® Rescue\*** and **Placebo** to reduce the duration of each infectious rhinitis symptoms rated by the WURSS 21.
- To compare the efficacy of **Healsea® Rescue\*** and **Placebo** to reduce the use of concomitant medication (systemic antibiotics, antipyretics, mucolytics, decongestants).
- To compare the subject overall assessment on efficacy of **Healsea® Rescue\*/Placebo**.
- Safety: to assess systemic and local tolerance of **Healsea® Rescue\*** over the study period.

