## **7. Design of the clinical investigation**

### **7.1 General**

#### **7.1.1 Design type of clinical investigation**

This is a two-arm, double-blind, parallel group, randomized controlled trial (RCT).

The primary endpoint will be assessed once daily during the treatment period. After D8, the WURSS-21 will be assessed once daily until the subject feels not sick for two consecutive days.

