**Visit 2 (V2) – (Day 13-15): end of study**

The investigator or his/her delegated designee will:

- Perform a physical and clinical examination. A pharyngeal nasal swab will be performed by the investigator or by the delegated study nurse to check for absence or presence of SARS-CoV2.
- Validate adverse events pertinent in the context of the common cold and of additional study procedures /incidents linked to medical device use and concomitant medications reported in the e-diary and complete the e-CRF accordingly and report any new relevant safety events.
- Ask the patient to complete the WURSS-21 if he/she still has symptoms.
- Assessed the compliance to the treatment by weighting the device returned by the subject. In case of nasal spray dysfunction and attribution of a new treatment using the back-up randomization list, the compliance will be assessed by weighting both devices. If a nasal spray is lost, the investigator will ask the patient to specify the number of missed nasal spray use and will report the data into the e-CRF.
- Ask the patient to complete a satisfaction questionnaire.

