## 12. CHANGES IN THE CONDUCT OF THE STUDY OR PLANNED ANALYSIS

The cold symptoms' duration was defined in the protocol as the number of symptomatic days between D1 and the first day the subject reports not having the symptom for two consecutive days.

Furthermore, since several patients still reported having symptoms while they reported they did not feel sick anymore at the question 1 during the two last days of completion of the WURSS-21 questionnaire, their positive answers to the cold symptoms' items have been considered as non-significant. Consequently, the question 1 has been taken into account instead of the corresponding items to determine the end of the cold symptoms' duration, however only on the condition that the two last days of completion were consecutive.

If the two last days of completion were not consecutive, positive answers to cold symptoms' items are still considered as symptomatic, even if the two last answers to the question 1 are negative. The symptom ends at the last symptomatic day if the patient reported the absence of this symptom after this day. Otherwise, the duration of the symptom is censored at D15 or at the end of the study, whichever occurs first.

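### The diary stops when the patient feels not sick, but the duration endpoint needs each symptom's own end, so durations of lingering symptoms are cut short

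*Protocol*

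**What the plan says.** **Endpoint.** Protocol 6.3 sets the aim "to reduce the duration of each infectious rhinitis symptoms rated by the WURSS 21". The Synopsis ends a symptom, item by item, at "the first day the subject reports not having the symptom for two consecutive days". Protocol 7.1.4 says the same in substance. Both allow censoring at the end of the study.

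**When the diary stops.** Protocol 7.1.1 states: "After D8, the WURSS-21 will be assessed once daily until the subject feels not sick for two consecutive days". Protocol 7.4.1 (D9-D13/15) likewise continues it "until the subject feels not sick for two consecutive days", and the Synopsis, Protocol 7.1.3 and SAP 3 agree. The patient form in SAP 13.3 specifies that this means the first question. It also tells a patient who has already reached that point within D1-D8 to stop, whereas Protocol 7.4.1 (D1-D8) asks for daily completion. The flow-chart footnote, in both documents, has a different rule: "After D8, WURSS-21 until complete resolution of symptoms for 2 consecutive days".

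**V2 form.** Protocol 7.4.1 (Visit 2) says: "Ask the patient to complete the WURSS-21 if he/she still has symptoms". The Synopsis, the flow chart, Protocol 7.1.4 and SAP 3 instead ask for it only when 'not sick' has not been ticked on two consecutive days.

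**Analysis.** SAP 10.2.2 sets a recovery date: the first of the last two completed days, if these are consecutive and item 1 is negative. It drops symptom reports from that date on and places the event at the last symptomatic day before it. SAP 12 explains that "several patients still reported having symptoms while they reported they did not feel sick anymore" and that their positive symptom answers were considered non-significant. SAP 6.3.1 makes every result other than the primary one descriptive.

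**The concern.** The endpoint asks about ten separate symptoms (items 2-11), while collection is switched off by one global question. A patient can feel well and still cough. For that patient the diary closes before the end of the cough can be confirmed. The analysis then does not treat the cough as unfinished: it records it as ended before the first 'not sick' day.

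What is reported as symptom duration thus becomes, for lingering symptoms, the duration of feeling sick. This matters because Protocol 7.2.2 names shorter symptom duration as the device's principal action. If treatment changes how sick patients feel more than it changes individual symptoms, or the reverse, the truncation could differ between arms.

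**Working it through.** The plan gives no figure for the duration endpoint. Its sample size (180/(1 − 0.10) = 200) is for the AUC and has no bearing here. The check traces the rules day by day.

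**Notation.** R is the first of two consecutive 'not sick' days. The last diary day is R+1. L is the last day on which the symptom is truly present. The symptom is taken as present every day from D1 to L, so its true duration is L days.

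**1. Can the protocol's end be observed?** It needs absence on L+1 and L+2, both recorded. If the symptom is still present on R, then L ≥ R and L+2 ≥ R+2, which is after the last diary day. At most one absent day (R+1) is seen, so the criterion cannot be met from the diary.

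**2. What does the SAP record?** The recovery date is R. The last symptomatic day before it is R−1, so the duration is (R−1) − 1 + 1 = R−1 days, counted as an event whatever L is.

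**3. Worked patient (assumed days).** R = D9, last diary day D10, V2 on D14. The last column applies the V2 trigger of Protocol 7.4.1, with this as the only remaining symptom.

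| L | True duration | SAP, no V2 form | Shortfall | SAP, V2 form if symptom persists |
|---|---|---|---|---|
| D8 | 8 | event, 8 | 0 | event, 8 |
| D9 | 9 | event, 8 | 1 | event, 8 |
| D10 | 10 | event, 8 | 2 | event, 8 |
| D11 | 11 | event, 8 | 3 | event, 8 |
| D12 | 12 | event, 8 | 4 | event, 8 |
| D14 | at least 14 | event, 8 | at least 6 | censored, 14 |

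In the last row a V2 form makes the last two completed days D10 and D14. They are not consecutive, so there is no recovery date and the patient is censored. The same patient is an event at 8 days or censored at 14, depending on which V2 instruction the site follows.

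**4. Uncollected at-home days.** From R+2 to the day before V2, the count is V2 − R − 2.

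| Stop (R, R+1) | V2 on D13 | V2 on D15 |
|---|---|---|
| D7, D8 | 4 | 6 |
| D8, D9 | 3 | 5 |
| D11, D12 | 0 | 2 |

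**5. With a symptom-based stop.** The end is confirmed if L+2 falls no later than V2, that is, L up to D11 (V2 on D13) to D13 (V2 on D15). All four intermediate cases in the first table (L = D9 to D12) would then be observed with V2 on D14.

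**The case against.** - **The plan already contains a symptom-based rule.** The flow-chart footnote says so, and the sentence in Protocol 7.4.1 (D9-D13/15) opens by addressing patients whose symptoms persist. Both are true, but the design section, the procedures and the form the patient reads all end on item 1. The footnote is an unreconciled contradiction, not a cure.
- **V2 catches persisting symptoms.** Under one of two conflicting instructions it does. A single form shows presence or absence on one day and does not date the end.
- **Censoring can deal with it.** This stands in part. A reader might infer that the objective cannot be answered for these patients, or that no analysis can help. The documents do not support that: a symptom still present at the last diary day has a known minimum duration. What is lost is the end date. The SAP does not use the partial information either, since it counts an event.
- **The SAP made a clinical judgement.** This also stands. A reader might infer that the protocol's definition was dropped because end dates were missing. SAP 12 gives another reason, that these answers were considered non-significant, and it declares the change openly. Nor do the past-tense wording and the change of definition show that it was made with knowledge of treatment; Protocol 9.3 foresees a blind review before database lock.
- **The stakes are limited.** Correct: this is one secondary endpoint, with p-values for information only.

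**Conclusion.** The concern holds as a mismatch between the endpoint and the collection rule, made worse by conflicting wording and by an analysis that turns unfinished symptoms into events. For any symptom still present on the first 'not sick' day, with no earlier two-day absence, the protocol's end cannot be observed from the diary, and the SAP reports at most R−1 days. In the worked patient the shortfall is 1 to 4 days for symptoms ending on D9 to D12, and at least 6 days for one lasting to D14 without a V2 form.

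The overall size cannot be computed, because the number affected is given only as several and is not split by arm. The gap in collection also varies by patient: 3 to 5 at-home days for a D8/D9 stop, fewer for later stops and more for stops within D1-D8. A reader might infer a bias in favour of one arm or a threat to the trial's main conclusion. Neither follows from this point: the direction is unknown and the endpoint is descriptive.

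Assumptions: the patient follows the form and stops on R+1, and the symptom is continuous from D1.

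**What to change.** **1. One collection rule**, worded identically in the protocol text, flow chart, e-diary and SAP 13.3:
- WURSS-21 daily through D8 for everyone.
- Then daily until items 2-11 are all marked absent on two consecutive days, or until V2.
- V2 form required whenever that condition has not been met.

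**2. For data collected under the item 1 rule** (SAP 12 indicates that such data exist, and rule 1 cannot recover them):
- Right-censor any symptom still present at the last diary day. If a later V2 form shows it absent, treat the end as interval-censored between the two dates; if the form shows it present, censor at V2.
- State how a symptom absent only on the last diary day is handled, since the two-day criterion is then unconfirmed.
- Use medians and a test that take censoring into account; the plain Wilcoxon-Mann-Whitney comparison in SAP 10.2.2 does not.
- Keep the item 1 recovery rule as a sensitivity analysis.
- Report the number of patients and symptoms affected, by arm.

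**Cost.** Wording, one e-diary trigger and some extra programming. Patients complete a few more evening questionnaires, in a diary they already open daily for adverse events and medication. Some will continue to V2 for a symptom, such as tiredness, that may not be due to the cold. Censoring has its own weakness: patients stop because they feel better, so their remaining symptoms may end sooner than those of patients still reporting. This is why both analyses should be shown.

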**Visit 2 (V2) – (Day 13-15): end of study**

The investigator or his/her delegated designee will:

- Perform a physical and clinical examination. A pharyngeal nasal swab will be performed by the investigator or by the delegated study nurse to check for absence or presence of SARS-CoV2.
- Validate adverse events pertinent in the context of the common cold and of additional study procedures /incidents linked to medical device use and concomitant medications reported in the e-diary and complete the e-CRF accordingly and report any new relevant safety events.
- Ask the patient to complete the WURSS-21 if he/she still has symptoms.
- Assessed the compliance to the treatment by weighting the device returned by the subject. In case of nasal spray dysfunction and attribution of a new treatment using the back-up randomization list, the compliance will be assessed by weighting both devices. If a nasal spray is lost, the investigator will ask the patient to specify the number of missed nasal spray use and will report the data into the e-CRF.
- Ask the patient to complete a satisfaction questionnaire.

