**Strictly Confidential**

	
 
with Healsea® Rescue*, 2 puffs in each nostril 2 times per day during 7 days (14 intakes of the investigational device).
 
 
or
 
 
with isotonic nasal spray (Placebo), 2 puffs in each nostril 2 times per day during 7 days (14 intakes of the Placebo).
 
 
- Part 2 (D9-D13/15): follow-up phase.
 
Visit 1 (V1) - (Day 1): Screening/Inclusion/Randomization Information and consent, demographic data and medical history, ongoing medication, physical and clinical examination (including COVID-19 antigen test), inclusion/non-inclusion criteria, randomization, e-diary presentation (including the first study questionnaire completion), reporting of adverse events, dispensation of Healsea® Rescue* Nasal Spray or Placebo (Isotonic nasal spray) (according to randomization list).
 
D1-D8 (at home): Daily completion of the electronic diary (questionnaire, adverse events/incidents and concomitant medications), Healsea® Rescue* /Placebo nasal spray treatment daily administration.
 
D8 (Telephone call): End of Healsea® Rescue*/Placebo nasal spray treatment.
 
D9-D13/15 (at home): Daily completion of the electronic diary (adverse events/incidents, concomitant medications, WURSS-21 if applicable, until the subject feels not sick for two consecutive days).
 
Visit 2 (V2) – (Day 13-15): end of study Physical and clinical examination (including COVID-19 antigen test), diary review, reporting of adverse events and incidents, compliance, subject satisfaction, WURSS-21 completion if the patient has not ticked “not sick” for 2 consecutive days in the previous days.

Number of Subjects:	A sample of 180 subjects (90 subjects per group) will be needed to provide 80% power with a 1-sided test at a 0.05 significance level to detect a difference between Healsea® Rescue* and Placebo groups AUC of 30%. Assuming that approximately 10% of subjects may drop-out the study, 200 will be randomly assigned at a ratio 1:1 to Healsea® Rescue* and Placebo (100 subjects per group).
Target Population:	Adults with acute infectious rhinitis

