#### 7.1.4 Secondary Endpoints with methods and timing for assessing, recording and analysing variables

**--AUC of the symptoms sub-score (items 2-11) and Quality of Life sub-score (items 12-20) of the WURSS-21 during first 8 days**

**- Duration of cold symptoms** in both groups assessed by means of the WURSS-21.

For each item, the duration is defined as the number of symptomatic days between visit V1 and the first day the subject reports not to have this symptom for two consecutive days.

To be noticed that the duration may be censored at the end of study participation (visit V2). Should the patient have not ticked "not sick" for 2 consecutive days at the end of study visit, a WURSS-21 will be completed by the patient during the visit.

*Strictly Confidential*

- **Frequency and number of days of concomitant treatments use** that may affect common cold symptoms (antipyretics, systemic or local mucolytics, decongestants, antitussives, antibiotics).

By reducing duration of common cold symptoms, Healsea® Rescue\* will very likely reduce the use of common rescue medication. Concomitant treatments use will be reported in the e-diary by the patient throughout the study, validated by the investigator at the end of study visit before being reported in the e-CRF.

- **Subject satisfaction** regarding ease of use, efficacy, local tolerance and taste at end of study visit (V2) using a **4-points categorical scale** and of the **Global subject feedback** on treatment use ("will you recommend the prescribed treatment for treatment / prevention of acute rhinitis?").

Although subjective, these endpoints are pertinent because Healsea® Rescue\* is an OTC product which does not require physician prescription.

- **Safety:** Assessment of adverse events and incidents throughout the study in both groups. Adverse events/incidents will be reported in the e-diary by the patient, validated by the investigator at the end of study visit before being reported in the e-CRF.

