#### - Day 1 (D1) - Day 8 (D8) (at home):

Daily completion of the electronic diary (questionnaire, adverse events/incidents and concomitant medications), Healsea® Rescue\* /Placebo nasal spray treatment daily administration.

- **D8 (Telephone call):**

End of Healsea® Rescue\*/Placebo nasal spray treatment.

- **Day 9 (D9) - Day 13 (D13)/Day 15 (D15) (at home):**

Daily completion of the electronic diary (adverse events/incidents, concomitant medications, WURSS-21 if applicable, until the subject feels not sick for two consecutive days).

- **Visit 2 (V2) (D13/D15): end of study**

Physical and clinical examination (including COVID-19 antigen test), diary review, reporting of adverse events and incidents, compliance, subject satisfaction, WURSS-21 completion if the patient has not ticked “not sick” for 2 consecutive days in the previous days.

The maximal study duration for each patient is 15 days.

	Acute phase		Telephone call	Follow-up	
	Screening/Inclusion	At home		At home	End of study
Visit name	V1		TC1	V2	
Visit Number				D9-End of study visit	
Days/Weeks	D1	D1-D8	D8	D13-D15	
Informed consent	X				
Eligibility criteria	X				
Demography and Medical history	X				
Physical and clinical examination	X				X
COVID-19 antigen test	X				X
Ongoing medication	X				
Randomization	X				
Treatment (Healsea® Rescue* or Placebo) (14 intakes)		X			
Telephone call (End of Healsea® Rescue* or Placebo)			X		
Subject e-diary and WURSS 21	X*	X		X §	X*
(Serious) Adverse Events/ (serious) incidents and concomitant medication reporting	X	X		X	X
Satisfaction Questionnaire					X
Compliance					X

§ After D8, WURSS-21 until complete resolution of symptoms for 2 consecutive days.

\*WURSS-21 to be completed with the investigator on site at screening and at the end of the study if the patient still has not ticked “not sick” for 2 consecutive days in the previous days.

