**Cold symptom's duration (days) = Last symptomatic day – first symptomatic day + 1**

For a given symptom, a symptomatic day is a day the patient gave an answer other than negative to the corresponding question (“do not have this”). Missing answers will be imputed by the LOCF.

The considered symptomatic days are between D1 and either D15, or the end of the study, or the day before the recovery date, whichever occurs first. Symptomatic days from the recovery date will not be taken into account.

For each of the items 2 to 11 of the WURSS-21 questionnaire, the origin date will be the date of the first symptomatic day.

The considered event is the end of the symptom.

For patients who reported a negative answer to the corresponding question on the last day they answered to it, or for patients with a recovery date, the event date will be the last symptomatic day before his/her last day of completion of the questionnaire, or before the recovery date if it exists.

Patients who did not report a negative answer to the corresponding question on the last day they answered to it, and without recovery date, will be censored at D15 or at the end of the study, and the censoring date will be the date of D15 or the reference end date, whichever occurs first.

For patients who never reported the presence of a given symptom (never ticked “very mild”, “mild”, “moderate” or “severe”) and having completed the questionnaire at D1, the origin date for the symptom will be D1, the symptom will be censored at D1 and the corresponding duration will be zero. If patients who never reported the presence of a given symptom did not complete the questionnaire at D1, neither origin date nor censoring date will be defined for this symptom and the corresponding duration will be missing.

For each of the items 2 to 11 of the WURSS-21 questionnaire, duration endpoints will be summarized using the medians, with 95% confidence intervals (CIs) for the medians by group. Results for Healsea® Rescue\* group and Placebo group will be compared using Wilcoxon-Mann-Whitney test. Subjects will be analysed on the FAS.

For each duration, boxplots will be realized by treatment group. Numbers of available data and p-values will be printed on the figure.

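### The closing WURSS-21 at V2 is triggered by symptoms in Protocol 7.4.1 but by the lack of two consecutive 'not sick' days elsewhere, and the SAP duration rule can then score the same patient at 7 or 14 days

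*Protocol*

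**What the plan says.** Two conditions decide who fills in the last WURSS-21.

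- **Symptom rule.** Protocol 7.4.1, in the list of V2 tasks: "Ask the patient to complete the WURSS-21 if he/she still has symptoms".
- **Two-day rule.** The Protocol synopsis has "WURSS-21 completion if the patient has not ticked “not sick” for 2 consecutive days in the previous days", and SAP section 3 repeats it for V2 ("WURSS-21 completion if the patient has not ticked"). The footnote to the Protocol flow chart asks for the form "at the end of the study if the patient still has not ticked" the 'not sick' box on two consecutive days. Protocol 7.1.4 makes the same condition explicit for the duration endpoint: if it is not met "for 2 consecutive days at the end of study visit, a WURSS-21 will be completed by the patient during the visit".

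Between D9 and V2 the patient keeps completing the WURSS-21 at home "until the subject feels not sick for two consecutive days" (Protocol 7.4.1). A compliant patient who recovers around D8 therefore has several days without a form before V2 on D13-D15.

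SAP 10.2.2 then scores the duration of items 2 to 11 from the forms that exist. The recovery date is the first of the last two answered days, provided that both are 'not sick' and that they are consecutive. The censored group is: "Patients who did not report a negative answer to the corresponding question on the last day they answered to it, and without recovery date". Their censoring date is D15 or the end of study, whichever comes first.

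**The concern.** Having a symptom and lacking two 'not sick' days are different conditions, so the two rules can ask different patients for the closing form. Because the SAP recovery date looks at the *last* two answered days, one extra form after a gap can remove a recovery date that the diary had already established. One form fewer can turn an ended symptom into a censored one.

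The endpoint at stake is the duration of each symptom, which serves the first-listed secondary objective. SAP 10.2.2 compares durations by the Wilcoxon-Mann-Whitney test and states no separate handling of censored values, and the mock duration table has no row for them. A value censored at V2 would, as written, enter as an ordinary duration near the top of the range.

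**Working it through.** The documents state no duration figure to reproduce. The check applies the SAP 10.2.2 rules to example patients under each trigger.

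**Inputs**
- First symptomatic day D1 (assumed); V2 on D14, inside the D13-D15 window of the flow chart.
- Duration = last symptomatic day − first symptomatic day + 1 (SAP 10.2.2).
- Recovery date as described above. Symptomatic days from that date on are ignored (SAP 10.2.2).
- Event if the last answer to the item is negative or a recovery date exists; otherwise censored at D15 or end of study, here D14 (SAP 10.2.2).

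**Results**

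| Patient | Two-day rule | Symptom rule (7.4.1) |
|---|---|---|
| 1. Symptom D1-D7, 'not sick' D8 and D9, diary stopped as instructed, symptom present at V2 | No form. Last two answered days D8, D9; recovery date D8; last symptomatic day D7. 7 − 1 + 1 = **7, event** | Form completed. Last two answered days D9, D14, not consecutive; no recovery date; last answer positive. 14 − 1 + 1 = **14, censored** |
| 2. Diary stopped at D7 (or D8) with the symptom present and no two 'not sick' days; symptom-free at V2 | Form completed, negative. 7 − 1 + 1 = **7** (or 8 − 1 + 1 = **8**), event; if LOCF fills the empty days to D13, 13 − 1 + 1 = **13**, event | No form; last answer positive. 14 − 1 + 1 = **14, censored** |
| 3. Diary complete to the day before V2 | Difference between the rules: 0 to 2 days | |
| 4. Last diary answer for the item already negative, symptom-free at V2 | No difference | No difference |

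**Sensitivity**
- Patient 1 gives the same result whether the item was absent or still ticked on the two 'not sick' days, and LOCF does not change it. Moving the pair to D9-D10 gives 8 against 14.
- V2 on D13 or D15 replaces 14 by 13 or 15.
- Patient 2 depends on LOCF. SAP 10.2.2 carries missing answers forward without saying whether this covers days with no form at all. SAP 6.4.6 rules that out, but for scores.
- The largest difference in row 3 arises with the symptom present to D13, 'not sick' ticked on D13, and 'not sick' and symptom-free at V2. With the form the recovery date is D13 and the duration 12 − 1 + 1 = 12; without it, 14 censored.

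**The case against.** **The 7.4.1 bullet may be shorthand.** It says 'if', not 'only if', and the Protocol elsewhere treats symptoms and feeling sick as one thing: the flow chart describes the home stopping rule as resolution of symptoms for two days. The flow chart also directs sites, so nobody can say that 7.4.1 alone was followed. This stands in part. Patient 2 needs the 'only if' reading. Patient 1 needs only the literal 'if'.

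**Patient 2 is not compliant.** He or she stopped the diary while symptomatic, and the missing diary is then the main problem. This stands. Nor is 7 or 8 known to be right, because the symptom ended at some unrecorded time before V2.

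**The SAP, not the bullet, causes the loss of the recovery date.** SAP 12 says openly that positive answers count when the last two completed days are not consecutive, and a cough present at V2 is not plainly an artificial value. Under the Protocol's own definition, which stops at the first two consecutive days without the symptom, the examples need not differ. This stands too, and is why one protocol sentence is not enough. But it does not remove the conflict: the same patient with the same course still gets two values, depending on which passage the site read.

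**A reader might infer from SAP 12 that patients like patient 1 are known to exist.** The text does not go that far. It reports several patients with symptoms on their last two completed days while answering 'not sick'. It does not report symptoms at V2 days later, or a V2 form filled in after a recovery date.

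**Conclusion.** The point holds as an inconsistency in data collection that reaches the values of a secondary endpoint. For a compliant patient it can move a symptom duration from a 7-day event to 14 days censored (V2 on D14). For a patient who stopped the diary early, the gap is 6 to 7 days without LOCF on empty days (14 − 8 = 6, 14 − 7 = 7) and 1 day with it. These figures rest on the SAP 10.2.2 rules as written and on a gap in the diary before V2. Without such a gap, the difference is at most 2 days.

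The reach is limited. The primary AUC stops at D8 and does not use V2 (SAP 6.4.7). SAP 6.3.1 makes all results other than the primary one descriptive. The documents do not say how many patients are affected. A reader might go further and infer a measurable loss of power for the duration comparison. The documents do not support that: they give neither the share of such patients nor the distribution of durations, and a comparison of contaminated with clean data would not compare one trigger with the other. The passages should be reconciled; the main conclusion of the trial does not depend on it.

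**What to change.** 1. **Protocol 7.4.1, V2.** Replace the bullet by the condition used in the synopsis, the flow chart, section 7.1.4 and SAP section 3: the patient completes the WURSS-21 at V2 unless two consecutive 'not sick' days have already been recorded, whether or not symptoms are present.
2. **SAP 10.2.2.** For forms already collected under the present bullet, state that a V2 form completed after two consecutive 'not sick' diary days does not cancel that recovery date. This agrees with the existing rule that symptomatic days from the recovery date on are ignored. The paragraph of SAP 12 on non-consecutive last days needs the same exception.

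The cost is one protocol sentence, one SAP sentence with its echo in section 12, and one more form for a few symptom-free patients at a visit that they already attend. The change does not settle whether LOCF covers days without any form; that question remains for patients who stopped the diary early.
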